5.3 Stratification Factors and Treatment Assignment

400 patients will be randomized 1:1 into either Arm 1 (short-course PMRT) or Arm 2 (long-course PMRT).

Randomization will be stratified by treatment center and age of the patient (<45 vs. ≥45).

6. RADIATION THERAPY

6.1 Radiation therapy schedule

Radiation therapy will be delivered to all intended fields, once daily, excluding holidays, weekends, and unavoidable factors limiting machine or patient availability.

Conventional fractionation: 25 fractions of radiation therapy (daily, Monday through Friday) to the chest wall with or without internal mammary nodes, and 23-25 fractions to the supraclavicular (with or without axillary) lymph nodes. Each fraction will consist of 200 cGy per day. Total dose = 5000 cGy to the chest wall and 4600-5000 cGy to the lymph nodes.

Hypofractionation: 16 fractions of radiation therapy (daily, Monday through Friday) to the chest wall with or without internal mammary nodes, and 15 fractions to the supraclavicular (with or without axillary) lymph nodes. Each fraction consists of 266 cGy per day. Total dose = 4256 cGy to the chest wall and 3990 cGy to the lymph nodes.

6.2 Radiation technical factors

- Radiation will be delivered with megavoltage (MV) equipment at energies of 6MV or higher.
- Protons are not permitted.
- Bolus to the mastectomy scar or chest wall will be prescribed at the discretion of the treating physician.
- No boost dose to the scar or other areas of the reconstructed chest wall is permitted.
- No deflation or expansion of tissue expander(s) should occur between simulation and radiation treatment completion.

6.3 Radiation simulation

Simulation will be CT-based. Patients will be positioned supine on the planning table in a customized immobilization device as per institutional protocol. Techniques to limit radiation dose to the heart, such as deep inspiration breath hold (DIBH) or gating are encouraged.

6.4 Treatment planning

The target volume will be the chest wall, tissue expander (or implant), and any associated nodal stations as per physician discretion. Delineation of these volumes will be as per institutional protocol. Per FABREC Trial protocol, microscopically positive margins are permitted. Per FABREC Trial protocol, giving PMRT solely for margins and not to treat nodes is permitted.

Lung and heart volumes will be limited as per institutional protocol. Maximum separation will be recorded. Location of mastectomy incision will be recorded.

Inhomogeneity will be limited to 110% in the chest wall, recording volume above 107%. Efforts will be made to strive for a maximum of 107% in hypofractionated cases (110% permitted). Inhomogeneity in the supraclavicular (+/-axillary) field will be limited to 110%. 3D-conformal RT or IMRT are permitted. There is no specified maximum dose on the composite plan. The composite plan may exceed 110%. Individual plans for the chest wall or lymph nodes must not exceed 110% inhomogeneity.

6.5 Treatment verification

For 3D-CRT and IMRT, quality assurance filming should be done per local, institutional protocol and does not need to be submitted to the sponsor. Dose distribution images and treatment planning fields should be kept by the treating institution for review by the sponsor, if

needed.

6.6 Compliance criteria

If inhomogeneity constraints are not attainable in the hypofractionated setting, the patient will be treated with standard fractionation as per protocol. Switching arms in this case is permitted, and these participants who switch arms will still be asked to complete all patient questionnaires and will be followed for 10 years. If the site plans to have a participant switch arms, the site must submit the Change in Study Status CRF via InForm 2 business days **prior** to the switch which will give the Study Chairs time to pre-approve the switch. Sites will be notified via email if approved.

6.7 Radiation quality assurance review

The Study Chairs will oversee quality assurance reviews for all participants treated on protocol. RT quality assurance review will be ongoing and performed remotely. RT quality assurance reviews will be facilitated by the study chairs and the study staff. The CSC will obtain the radiation therapy data from the Inform database for the Study Chairs to review and assess.

6.8 Radiation adverse events and reporting

All participants will be seen weekly, according to their treatment plan, by an attending radiation oncologist while undergoing treatment. Side effects will be recorded and managed using clinical discretion. For information about adverse events, see Adverse Event Reporting section of protocol. Details on the adverse event reporting can be found in the AE section of the protocol.

6.9 RT Modifications

Treatment breaks should be kept to a minimum but do not constitute protocol violations.

Changes in RT dose will constitute major protocol violations.

6.10 Supportive Care

Supportive care is permitted and is at the discretion of the treating investigator.

7. ADVERSE EVENTS REPORTING REQUIREMENTS

Adverse event (AE) monitoring and reporting is a routine part of every clinical trial.

Summary of how to collect and report adverse events (AEs) for the FABREC trial:

1. **Standard Care** All patients will be seen per their treatment plan by an attending radiation oncologist while undergoing treatment. **All adverse events** should be recorded in the patient's medical record per standard practice at your site and managed using clinical discretion. On the Medical Record Review CRFs for the FABREC Study, Clinical Research Professionals (CRPs) will be asked to report AEs as documented in the patients' charts; these medical record reviews will be done at pre-specified timepoints.
2. **Routine Solicited Adverse Events** will not be collected for the FABREC Trial.
3. **Reportable Serious Adverse Events** should be reported using the FABREC Serious Adverse Event CRF each time a reportable SAE occurs. These CRFs should be submitted using InForm. For a list of reportable SAEs, see below.

7.1 **Routine Adverse Events**

Routine Adverse Events will not be collected for the FABREC Trial. **Only events outlined in Section 7.2 should be reported via InForm.**

7.2 **Reportable Serious Adverse Events**

Reportable Serious Adverse Events that occur at any time between initiation of PMRT and 3-years after the initiation of PMRT must be reported using the FABREC Serious Adverse Event CRF. In general, the CRF should be submitted via InForm within 5 calendar days of the AE date. When an adverse event occurs at an institution outside the enrolling site, there may be a delay between when an adverse event occurs and when the study team is alerted to the event. In these instances, it is acceptable for the study team to submit those adverse events in InForm within 5 calendar days of being notified about the event and will not incur a violation.

Only "reportable SAEs" require reporting. For the FABREC trial, a reportable SAE is defined as:

- Grade 1, 2, or 3 **brachial plexopathy** (per NCI CTCAE v 4.03, this AE does not have grade 4 or 5)
- Grade 3 **chest wall pain** (per NCI CTCAE v 4.03, this AE does not have grade 4 or 5)
- Grade 3 **lymphedema** (per NCI CTCAE v 4.03, this AE does not have grade 4 or 5)
- Grade 3, 4, or 5 **myocardial infarction**
- Grade 1, 2, 3, 4, or 5 **pneumonitis**

- Grade 3, 4, or 5 **treatment related secondary malignancy**
- Grade 3, 4, or 5 **wound infection**
- Unexpected grade 3 or 4 with a possible, probable or definite attribution to PMRT
- Grade 5 (death); all deaths on study require expedited reporting regardless of attribution or causality.
- Local/regional recurrence (not in NCI CTCAE v4)
 - **Note:** We are only interested in following participants who experience local/regional recurrences. When participants experience distant recurrences, they should be withdrawn from the study and all follow-up should be discontinued as these patients may not be monitored for local/regional recurrences due to distant disease.

NCI CTCAE v4 can be downloaded from

http://ctep.cancer.gov/protocolDevelopment/electronic_applications/ctc.htm

Only the events listed above need to be reported in InForm. Events that fall outside the list above do not need to be reported in InForm.

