5. REGISTRATION AND RANDOMIZATION PROCEDURES

5.1 Registration Process for all sites

This section applies to DF/HCC Institutions (Dana-Farber/Harvard Cancer Center) and all other investigative sites.

To register a participant on the FABREC Trial, please follow these steps:

- Each participating site should identify eligible participants at their site.
- The consenting investigator should approach the patient and hold an informed consent discussion.

- If the potential participant agrees to participate, the consenting investigator and the patient should both sign the Informed Consent document.
- The study staff should then send the following documents to the Central Study Coordinator (CSC) via secure email to [contact] or via fax to [contact] (be sure to write ATTENTION: FABREC Central Study Coordinator on your fax cover sheet).
 1. Signed Informed Consent Form (all pages)
 2. Signed HIPAA authorization form (if applicable: At some sites the HIPAA authorization form and the informed consent document are two separate documents. At other sites, the HIPAA authorization form is contained within the informed consent document, so only the informed consent document need be submitted)
 3. Completed Eligibility Checklist
- The CSC will review the eligibility checklist to ensure that all fields are complete and that all values are within the acceptable range allowed by the protocol. If any information is missing, the CSC will contact the site.
- Next the CSC will work with the Dana-Farber Office of Data Quality (ODQ) to register and randomize the participant.
- Within 24 business hours*, the CSC will email the following information to the site:
 1. Confirmation that the participant has been successfully registered
 2. The participant's unique study ID number
 3. The arm to which the participant was randomized

*Business hours for this study are defined as: Monday through Friday from 8:00 AM to 5:00 PM Eastern Time, not including holidays.

If you need expedited assistance during normal business hours (Eastern Standard Time), please contact the FABREC Central Study Coordinator at [contact] or [contact].

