7.4 AE Data Collection and Definitions

AE, date of event, grade, attribution, and relation to an underlying disease or condition will be collected for each AE and SAE.

Grade:

- Grade 1 - Mild AE
- Grade 2 - Moderate AE
- Grade 3 - Severe AE
- Grade 4 - Life-threatening or disabling AE
- Grade 5 - Death related to AE

Attribution:

- Definite – The AE *is clearly related* to the study treatment.
- Probable – The AE *is likely related* to the study treatment.
- Possible – The AE *may be related* to the study treatment.
- Unlikely – The AE *is doubtfully related* to the study treatment.
- Unrelated – The AE *is clearly NOT related* to the study treatment.

Study treatment = PMRT

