9.1 Summary of data collection and submission

Acronyms used in following table: CRP = Clinical Research Professional (at enrolling site) CSC = Central Study Coordinator (sits at lead site, Dana-Farber)		
Timepoint	Data to be collected	Who's responsible? How to Collect & Submit data?
Enrollment (after participant signs informed consent but before protocol treatment begins)	➤ Eligibility checklist	Site CRP should: ➤ Fax or securely email the eligibility checklist, all pages of the signed informed consent form, and the HIPAA authorization form (if it is a separate document from the ICF) to the CSC . CSC will: ➤ Email site with participant's unique study ID and treatment arm randomization within 24 business hours. ➤ Enter Eligibility Checklist data into InForm
	➤ Baseline Patient Questionnaire	Site CRP should: ➤ Administer questionnaire to patient ➤ Submit patient responses via InForm ➤ Keep paper original at your site CSC will: ➤ Send participant \$50 gift card upon receipt
Baseline (after enrollment but before protocol treatment begins)	➤ Baseline Medical Record Review CRF	Site CRP should: ➤ Submit electronically via InForm
	➤ Reconstruction photographs	Patient or Clinician should: ➤ Take reconstruction photographs Patient or Clinician or Site CRP should: ➤ Send photographs to CSC electronically via secure file transfer protocol (FTP). Contact the CSC for detailed FTP instructions.
	➤ Cosmetic Outcomes CRF	Study Chair (or delegate) will: ➤ Evaluate photos ➤ Submit the Cosmetic Outcomes CRF via InForm
<= 30-days after PMRT ends	➤ Off Treatment CRF	Site CRP should: ➤ Submit electronically via InForm
Ongoing from initiation of PMRT through 3-years after date of PMRT initiation	➤ Serious Adverse Event (SAE) Reporting CRF	Site CRP should: ➤ Enter SAE into InForm ONLY when a reportable event occurs ➤ Submit within 5 calendar days of start of SAE ➤ For a list of "reportable SAEs," see the AE section of protocol.
6-months (defined as 6-months after initiation of PMRT)	➤ 6-month Patient Questionnaire	CSC should: ➤ Administer patient questionnaire ➤ Enter patient responses into InForm ➤ Send participant \$50 gift card
	➤ Reconstruction photographs	Patient or Clinician should: ➤ Take reconstruction photographs Patient or Clinician or Site CRP should: ➤ Send photographs to CSC electronically via secure file transfer protocol (FTP). Contact the CSC for detailed FTP instructions.

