We will analyze adverse events toxicities experienced by all patients on the study. Adverse event rates will be summarized by types of adverse event (serious/non-serious, grade, and attribution) for each treatment arm, and they will be compared between the arms by using Fisher’s exact test. Toxicity data will be monitored by the DSMB every 6 months to assure safety of the participants (see Section 11).

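### Section 10f tests attribution-specific adverse event rates between arms although sites know the arm and no blinded adjudication is described; two of the ten reportable items in 7.2 are also filtered by a causal judgment

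*Combined protocol and SAP*

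**What the plan says.** **Reporting (7.2).** Ten kinds of event are reportable between the start of PMRT and three years later. Eight carry no condition on cause: brachial plexopathy, chest wall pain, lymphedema, myocardial infarction, pneumonitis, wound infection, death and local/regional recurrence. Pneumonitis, for example, is listed as "Grade 1, 2, 3, 4, or 5 pneumonitis", and for deaths the text is explicit: "all deaths on study require expedited reporting regardless of attribution or causality". The other two depend on a causal judgment. One is grade 3-5 "treatment related secondary malignancy". The other is "Unexpected grade 3 or 4 with a possible, probable or definite attribution to PMRT".

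**Who knows the arm.** Under 5.1 the registration email to the site includes "The arm to which the participant was randomized". Under 9.1 the site research professional is told: "Enter SAE into InForm ONLY when a reportable event occurs". The documents do not say who assigns attribution, and they describe no arm-blinded or central review of it.

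**What is recorded (7.4).** "AE, date of event, grade, attribution, and relation to an underlying disease or condition will be collected for each AE and SAE". Attribution has five levels, from definite to unrelated.

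**Analysis (10f).** "Adverse event rates will be summarized by types of adverse event (serious/non-serious, grade, and attribution) for each treatment arm". The same sentence says the rates are compared between arms with Fisher's exact test. It gives no alpha, no sidedness and no data source.

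**Other routes.** Section 7 has staff abstract adverse events from the charts at set timepoints, and Section 8 lists toxicities among the chart-review data. Annual follow-up in Section 8 tracks new malignancy for ten years. None of these carries an attribution condition. Section 7.1, however, says that routine adverse events are not collected and that only 7.2 events go into InForm.

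**The concern.** Randomization makes the rates of all events comparable between arms. It does not do so for events that someone who knows the arm has judged to be related. If the threshold for calling an event related differs between short-course and long-course patients, attribution-specific rates will differ even when toxicity is identical, and a real difference can be cancelled.

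This enters in two places. The first is the attribution breakdown in 10f, which is tested whatever the data source. The second is the pair of filtered items in 7.2. If 10f draws on the SAE form, an unexpected grade 3-4 event judged unlikely to be related is simply absent. That item is also the only one on the list that catches non-fatal toxicity nobody named in advance.

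What is at stake is part of Objective 2, which hypothesises no increase in side effects with the short course and names secondary malignancy among the rare effects to be monitored.

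**Working it through.** The plan states no adverse event rate, power or error rate for 10f, so there is no figure to reproduce. The calculation below shows how large the effect could be under stated assumptions.

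**From the documents:** 400 patients randomized 1:1, so 200 per arm (5.3); Fisher's exact test between arms (10f).

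**Assumed:** two-sided test at 0.05; all-cause rate p equal in both arms, at 2%, 5%, 10% or 20%; shares of events attributed to PMRT, q1 and q2, of 60% vs 40% or 70% vs 30%.

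**Formula.** The related-event rate in arm k is p × q_k. The chance of a significant result is the sum, over all counts i and j from 0 to 200, of Bin(i; 200, p·q1) × Bin(j; 200, p·q2), taken over the pairs where Fisher's p ≤ 0.05. This is exact enumeration, not simulation.

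**Example at p = 10%.** Each arm expects 200 × 0.10 = 20 events. At 60% vs 40% the related rates are 0.10 × 0.6 = 6% and 0.10 × 0.4 = 4% (12 vs 8 events, ratio 1.5). At 70% vs 30% they are 7% and 3% (14 vs 6 events, ratio 2.3).

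**Chance that Fisher's test is significant when true toxicity is equal:**

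| All-cause rate, both arms | All events | 60% vs 40% attributed | 70% vs 30% attributed |
|---|---|---|---|
| 2% | 1.7% | 0.9% | 2.2% |
| 5% | 2.9% | 4.7% | 14.7% |
| 10% | 3.4% | 10.2% | 36.9% |
| 20% | 3.7% | 21.4% | 72.1% |

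**Equal attribution.** At 60% in both arms the figures are 2.2%, 3.0% and 3.5% for rates of 5%, 10% and 20%. There is no inflation, so the problem needs attribution to differ by arm.

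**Masking.** Take true rates of 5% and 12%.
- All events: the chance of significance is 66%.
- 60% attributed in both arms (3.0% vs 7.2%): 40%.
- 80% attributed in the 5% arm and 40% in the 12% arm: the related rates are 0.05 × 0.8 = 4.0% and 0.12 × 0.4 = 4.8%, and the chance falls to 4%.

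**The case against.** **Scope.** A reader might infer that the trial's toxicity contrast as a whole reflects opinion. The documents do not support that. Eight of the ten reportable items have no attribution condition, including plexopathy, the other rare effect that Objective 2 names. Section 10f also breaks rates down by grade and seriousness.

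**Counted only if attributed.** A reader might also infer that unexpected events and malignancies enter the analysis only if attributed. That is true of the SAE form, but it is not shown for 10f. Chart review and annual follow-up are unfiltered, and the non-serious category in 10f implies a source beyond the SAE form. This stands. But 7.1 contradicts the chart-review text and 10f names no source. If 10f uses the SAE form, the filtered events are missing. If it uses chart review, the test by attribution remains.

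**Evidence of bias.** No passage says who assigns attribution. That it is the site is an inference, though a reasonable one, because the site must judge attribution to know whether a form is due. Section 1.2 describes clinicians as unsure about the new schedule and calls the conventional one both familiar and problematic. That makes a difference by arm plausible and gives it no direction.

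**Rates.** The two filtered items are residual categories and may be rare. At an all-cause rate of 2% or below, neither assumed split pushes the error above 5%. This stands and limits the size of the point.

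**Importance.** The 10f comparison is a secondary safety summary with no stated power or decision rule. The primary endpoint (PWB change at 6 months) and the recurrence stopping rule are unaffected. This also stands.

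**Conclusion.** The point holds for the attribution-based contrasts: the breakdown by attribution in 10f, and the two items in 7.2 that need a causal judgment before they reach the SAE form. In a trial where sites know the arm and no blinded adjudication is described, randomization does not protect these contrasts.

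The size depends on inputs that the documents do not give. Under the assumed splits, the chance of a spurious difference runs from 1-2% at a 2% all-cause rate to 21-72% at 20%, against 2-4% when all events are compared. The effect vanishes if attribution is equal in the two arms. A filter can also hide a real difference, as the masking example shows.

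The documents do not show that attribution will differ by arm, nor that the conclusion on side effects rests on these contrasts. The change is still worth making, because it is cheap and removes an avoidable source of bias.

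**What to change.** **In 10f:**
- Test between arms only on events regardless of attribution, by type, grade and seriousness. Present attribution by arm descriptively, without a test.
- For secondary malignancy, compare all new malignancies from annual follow-up, and state the time window, since that follow-up runs ten years and SAE reporting three.
- For unexpected grade 3-4 events, use the adverse events abstracted at chart review, whatever their attribution, and name chart review as the source.
- Where only the attribution-filtered SAE-form data exist, report them by arm descriptively. Do not drop them, since that would lose information on unforeseen toxicity.

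**In Section 7:** reconcile 7.1 with the chart-review text so that it is clear which adverse events are collected. The expedited-reporting rule in 7.2 can stay as it is.

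**Cost.** This is mostly wording in 10f and 7.1. If the chart-review forms do not already capture grade 3-4 events whatever their cause, collection must be extended, or those events can only be described. All-cause rates include unrelated events and are slightly noisier. Chart entries are still made by staff who know the arm, so the change removes the causal filter but not every effect of open treatment.
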